4.3. Safety Analysis Set

The Safety Analysis Set (SAF) will be defined as all subjects who receive at least one dose of study medication classified according to actual study treatment received. The safety analysis set is the primary population for treatment administration/compliance and safety. A randomized but not treated subject will be excluded from the safety analyses.

5. GENERAL METHODOLOGY AND CONVENTIONS

- The final analysis and reporting of results will be performed after the completion of the study and the database is locked.

5.1. Hypotheses and Decision Rules

PF-04965842 200 mg QD will be declared superior to placebo if the null hypothesis of no difference between PF-04965842 200 mg QD versus placebo for **both** co-primary endpoints is rejected at the 5% significance level. Similarly, PF-04965842 100 mg QD will be declared superior to placebo if the null hypothesis of no difference between PF-04965842 100 mg QD versus placebo for **both** co-primary endpoints is rejected at the significance level specified below.

A sequential Bonferroni-based iterative multiple testing procedure to strongly control the familywise Type 1 error at 5% will be used for testing each of the two PF-04965842 doses (200 mg QD and 100 mg QD) versus placebo on the primary and key secondary endpoints. The procedure belongs to a class of consonant multiple test procedures (Hommel et al. 2007) which are a subclass of the closed test procedures (Marcus et al. 1976).

[figure not shown]
The procedure will first test the Week 12 co-primary endpoints (IGA and EASI-75) for 200 mg QD vs placebo at a 5% significance level. If this hypothesis is not rejected, then no further testing will be conducted. If this hypothesis is rejected, then testing may continue on two paths depending on the testing for Week 2 NRS4 for severity for 200 mg QD vs placebo at a 2.5% significance level:

- If the hypothesis for the Week 2 NRS4 for severity for 200 mg QD vs placebo is rejected, then the unused alpha level of 2.5% will be passed on to a series of testing in

Sequence A (see Figure 2 below) at a 5% significance level. If any hypothesis in this sequence is not rejected, then the procedure stops.

- If the hypothesis for the Week 2 NRS4 for severity for 200 mg QD vs placebo is not rejected, then the series of testing in Sequence A (see Figure 2 below) will be tested at a 2.5% significance level. If any hypothesis in this sequence is not rejected, then the procedure stops. If all hypotheses in this sequence are rejected, then the unused alpha level of 2.5% will be passed on to the testing of hypotheses for Week 2 NRS4 for severity (200 mg QD vs placebo) at a 5% significance level.

Figure 2 Schematic for Multiple Testing Procedure

Hypotheses for all other endpoints not described here are to be tested at the nominal 5% significant level, without making adjustments for multiple comparisons.

5.2. General Methods

In general, number and percent will be presented for binary variables. Number, mean, standard deviation (or standard error of the mean), median, first and third quartiles will be presented for continuous variables.

Estimates of the difference in proportions along with the two-sided 95% confidence interval will be provided for the PF-04965842 200 mg QD group versus the PF-04965842 100 mg QD group. No hypotheses will be tested.

5.2.1. Analyses of Binary Data

Binary data at each scheduled visit will be analyzed by two approaches: (1) the test of hypothesis (and the p-value) between the PF-04965842 treatment groups versus the placebo group will be conducted by the Cochran-Mantel-Haenszel (CMH) statistic adjusting for the effect of randomization strata; p-values from the CMH statistic will be used to establish the superiority of each dose of PF-04965842 to placebo in binary responses; and (2) the proportion of responders in the PF-04965842 treatment groups versus the placebo group will be summarized by the difference and its 95% confidence interval obtained by normal approximation. The difference in proportions will be calculated within each randomization stratum. The final estimate of the difference in proportions will be a weighted average of these stratum-specific estimates using CMH weights. The CMH weight w_k for stratum k ($k = 1, 2, 3, 4$) is given by,

$$w_k = \frac{\frac{n_{ik} n_{ck}}{n_{ik} + n_{ck}}}{\sum_{j=1}^4 \frac{n_{ij} n_{cj}}{n_{ij} + n_{cj}}}$$

where n refers to sample size, the subscript c refers to a comparator group (eg, placebo) and the subscript i refers to a test group (eg, either the low or high doses (so that two test statistics are calculated, one for each dose versus placebo). The difference is estimated as $\hat{d} = \sum_{k=1}^4 w_k (\hat{p}_{ik} - \hat{p}_{ck})$, where \hat{p} refers to the estimated relative frequency. An estimate for \hat{p} is obtained as x/n , where x is the number of responders.

Two-sided 95% confidence intervals for the difference (based on a normal approximation) are formed by:

$$\hat{d} \pm 1.96 \sqrt{\sum_{k=1}^4 w_k^2 \left(\frac{\hat{p}_{ik}(1 - \hat{p}_{ik})}{n_{ik}} + \frac{\hat{p}_{ck}(1 - \hat{p}_{ck})}{n_{ck}} \right)}$$

In the above formula for the variance of \hat{d} (under the square-root sign), when the number of responders is zero ($x = 0$), then \hat{p} will be replaced by $0.5/(n + 1)$. This change will be made only for calculating the variance of \hat{d} and not anywhere else. Estimates of the difference in proportions along with the two-sided 95% confidence interval will also be provided for the PF-04965842 200 mg QD group versus the PF-04965842 100 mg QD group. No hypotheses will be tested. In analyses of responders, 95% confidence intervals will be calculated for the estimated proportion of response. The confidence interval is based on the normal approximation (or the Clopper-Pearson exact method when there are no or 100% responders).

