9.1. Sample Size Determination

Sample size for the study was based on the co-primary endpoints. A total sample of 375 subjects with 150 subjects randomized to PF-04965842 200 mg QD, 150 subjects randomized to PF-04965842 100 mg QD and 75 subjects randomized to placebo (2:2:1 randomization) would provide at least 95% power to detect a difference in IGA response rate of at least 20% between PF-04965842 200 mg QD (or PF-04965842 100 mg QD) and placebo, assuming the placebo response rate is 6% at Week 12. Furthermore, this will also provide at least 99% power to detect a difference in EASI-75 response rate of at least 30% between PF-04965842 200 mg QD (or PF-04965842 100 mg QD) and placebo, assuming the placebo response rate is 15% at Week 12.

The Type-I error for testing each individual co-primary endpoint was fixed at 5%. Since both endpoints are co-primary, the study will meet its primary endpoint only if both hypotheses (corresponding to each co-primary endpoint) are rejected. Therefore, the Type-I error rate remains controlled at 5% for testing the primary endpoint. The power to reject both hypotheses when a true difference exists (alternative hypothesis is true) could be at least 94% depending on the correlation between the endpoints.

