3.2.3. Other Efficacy Endpoints

- Response based on the IGA for clear (0) at all scheduled time points;
- Response based on a $\geq 50\%$, $\geq 90\%$ and $=100\%$ improvement in the EASI total score (EASI-50, EASI-90 and EASI-100) at all scheduled time points;
- Percent change from baseline at all scheduled time points in the EASI total score;
- Change from baseline in %BSA (from EASI) affected at all scheduled time points;
- Proportion of patients with %BSA (from EASI) $< 5\%$ at all scheduled time points;
- Response based on a $\geq 50\%$ and $\geq 75\%$ improvement in SCORAD (SCORAD50, SCORAD75) from baseline at all scheduled time points. A detailed description of the derivation of the SCORAD score is provided in [Appendix 7](#);
- Percent change from baseline at all scheduled time points in the SCORAD total score;
- Change from baseline at all scheduled time points in SCORAD subjective VAS assessments of sleep loss.

CCI [REDACTED]
[REDACTED]
[REDACTED]
[REDACTED]
[REDACTED]
[REDACTED]
[REDACTED]
[REDACTED]
[REDACTED]
[REDACTED]
[REDACTED]
[REDACTED]
[REDACTED]
[REDACTED]

C
C
I

[REDACTED]

[REDACTED]

[REDACTED]

[REDACTED]

[REDACTED]

[REDACTED]

[REDACTED]

[REDACTED]

[REDACTED]

[REDACTED]

[REDACTED]

[REDACTED]

[REDACTED]

[REDACTED]

[REDACTED]

[REDACTED]

[REDACTED]

[REDACTED]

[REDACTED]

[REDACTED]

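### Single-arm response-rate intervals use the normal approximation at every count except 0 and n; with 75 placebo subjects they under-cover at true rates of about 4–8%, and at 1–3 responders the lower limit is negative (minor, descriptive only)

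*SAP*

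**What the plan says.** SAP 5.2.1 states: "In analyses of responders, 95% confidence intervals will be calculated for the estimated proportion of response". It then gives the method: "The confidence interval is based on the normal approximation (or the Clopper-Pearson exact method when there are no or 100% responders".

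The SAP does not write out a formula for the single-arm interval. The normal-approximation formula it does display is for the treatment difference: "Two-sided 95% confidence intervals for the difference (based on a normal approximation) are formed by" the estimate plus or minus 1.96 times an unpooled standard error, which is a Wald interval.

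The same section has a small-count repair, replacing a zero proportion by 0.5/(n+1), but restricts it: "This change will be made only for calculating the variance of" the difference. No truncation at zero and no low-count rule is given for a single arm.

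The section covers binary data at each scheduled visit. Protocol 9.1 plans 75 placebo subjects, with the IGA calculation "assuming the placebo response rate is 6% at Week 12" and the EASI-75 calculation "assuming the placebo response rate is 15% at Week 12". SAP 3.2.3 adds stricter endpoints, for example "Response based on the IGA for clear (0) at all scheduled time points", and EASI-90 and EASI-100.

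**The concern.** A Wald interval is centred on the observed proportion and takes its width from that same proportion. When few responders are expected, a low observed count gives an interval that is both too low and too short. At 6% of 75 the expected count is 4.5, which is in that region.

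Switching to an exact interval only at 0 and n repairs the two counts where Wald has zero width. It leaves counts 1, 2, 3 and so on untouched, and it puts a jump between 0 and 1.

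What is at stake is the printed precision of low response rates, above all in the placebo arm. Readers would see some negative percentages, and an upper limit for placebo response that lies below the truth more often than 2.5% of the time.

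**Working it through.** **Inputs.** n = 75 placebo and 150 per active arm; placebo rates 6% (IGA) and 15% (EASI-75); differences of 20 and 30 points (Protocol 9.1). The interval rule is from SAP 5.2.1. Reading the normal approximation as Wald is an inference from the displayed formula for the difference.

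**The plan's own figures.** The documents give no coverage figure. Their power statements use the same inputs and reproduce (two-sided 5% assumed), with power = Φ[(Δ − 1.96·SE0)/SE1], where SE0 is pooled and SE1 unpooled.
- IGA, 6% vs 26%: pooled rate (4.5 + 39)/225 = 0.1933; SE0 = 0.0558; SE1 = 0.0451; (0.20 − 0.1095)/0.0451 = 2.01, so 97.8% (stated: at least 95%).
- EASI-75, 15% vs 45%: pooled rate 0.35; SE0 = 0.0675; SE1 = 0.0579; (0.30 − 0.1322)/0.0579 = 2.90, so 99.8% (stated: at least 99%).
- Both: 0.95 × 0.99 = 94.05% (stated: at least 94%).

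**Intervals at low counts, n = 75.**
- x = 0 (Clopper-Pearson): upper limit 1 − 0.025^(1/75) = 4.80%.
- x = 1: 1.33% ± 1.96·√(0.0133·0.9867/75) = 1.33% ± 2.60%, or −1.26% to 3.93%.
- x = 2: −0.98% to 6.31%.
- x = 3: −0.43% to 8.43%.
- x = 4: 0.25% to 10.42%, the first positive lower limit.

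The upper limit therefore falls from 4.80% to 3.93% when one responder is observed instead of none. At n = 150 the same step is 2.43% to 1.97%.

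**Coverage.** For a true rate p, coverage is the sum of the Binomial(75, p) probabilities of all x whose interval contains p. At p = 6% the upper limit is too low only for x = 0 and x = 1: 0.97% + 4.62% = 5.6%. The lower limit is too high in 0.5%. Coverage is 93.9%.

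| True rate | SAP rule | Upper limit below truth | Negative lower limit | Wilson | Clopper-Pearson |
|---|---|---|---|---|---|
| 1% | 99.9% | 0.0% | 52.2% | 96.0% | 99.3% |
| 2% | 99.9% | 0.0% | 71.7% | 93.6% | 98.3% |
| 3% | 99.8% | 0.0% | 71.0% | 97.5% | 99.3% |
| 4% | 85.1% | 14.6% | 60.0% | 97.0% | 99.0% |
| 5% | 89.0% | 10.6% | 45.8% | 94.5% | 96.6% |
| 6% | 93.9% | 5.6% | 32.5% | 95.5% | 97.6% |
| 7% | 89.7% | 9.7% | 21.7% | 96.0% | 98.1% |
| 8% | 93.9% | 5.5% | 13.8% | 95.0% | 97.0% |
| 15% | 93.2% | 5.4% | 0.2% | 95.0% | 96.3% |

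On a fine grid from 4% to 8% the SAP rule is below 95% at every point (mean 90.2%, minimum 85.1%). Wilson has mean 95.4% and minimum 92.9%; Clopper-Pearson has mean 97.4% and minimum 95.5%.

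The result does not depend on n being exactly 75: for n from 68 to 78, coverage at 6% runs from 91.3% to 94.5%. In the active arms at their planning rates (n = 150) there is almost no shortfall: 94.6% at 26% and 95.1% at 45%.

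**The case against.** The strongest case on the other side has four parts.

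1. **A reader might infer that the rule under-covers at all low rates, and worst for IGA clear, EASI-100 and early visits.** The enumeration does not support that. At 1–3% the rule over-covers, because no upper limit is ever below 3.93%. IGA clear and EASI-100 cannot be more frequent than IGA response and EASI-75 at the same visit, but the documents give no rates for them; 1–3% is an assumption. This objection stands, and it limits the coverage claim to rates of about 4–8% and, slightly, 15%.

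2. **The 85% figure sits just past a discontinuity.** Coverage is 99.8% at 3.8% and 85.1% at 4.0%, because 4% lies just above the upper limit for 1/75. At the two planning rates the shortfall is only 1–2 points. That is right, but 6% is itself near a local peak: between 5% and 7% mean coverage is 90.6% and the minimum 85.3%.

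3. **Nothing is decided on these intervals.** SAP 5.2.1 bases superiority on the CMH p-value, and the effect estimate has its own interval. This stands in full and sets the severity.

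4. **Wilson and Clopper-Pearson need an integer count.** Multiply imputed NRS4 rates and tipping-point rates have none after pooling (SAP 5.3.1, Appendix 3). This also stands, and the fix has to provide for it.

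The reversal is also uncommon at the planned IGA rate: at 6% the chance of 0 responders is 1.0% and of 1 responder 4.6%. At assumed rates of 1–3% the chance of 0 is 47% down to 10%.

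**Conclusion.** The rule as written gives single-arm intervals with wrong error bars at low counts. At n = 75, coverage is 85–94% for true rates of 4–8% (93.9% at 6%) and 93.2% at 15%, with most misses on the upper side. Lower limits are negative for 1–3 responders, and 1/75 has a smaller upper limit than 0/75. At 1–3%, if rarer endpoints fall there, the problem is confined to the negative limits and the reversal.

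The severity is minor. A reader might infer that the co-primary conclusions or the treatment-effect intervals are compromised. The documents do not support this: the CMH tests, the testing sequence, the power and the interval for the difference use none of these single-arm intervals.

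The conclusion assumes that the normal approximation is Wald without truncation, and that about 75 placebo subjects are analysed.

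**What to change.** In SAP 5.2.1, replace the sentence on the single-arm interval as follows.

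- **Rates from observed or non-responder-imputed data:** one method at every count, either Wilson score or Clopper-Pearson. Neither gives a negative limit, and both have upper limits that rise with the count: 4.87%, 7.17%, 9.21% (Wilson) and 4.80%, 7.21%, 9.30% (Clopper-Pearson) for 0, 1 and 2 of 75. This also covers NRS4 visits at which SAP 5.3.1 makes no imputation.
- **Multiply imputed NRS4 and tipping-point rates:** keep Rubin pooling, but form the interval on a transformed scale such as the logit: logit(p) ± critical value × SE/[p(1 − p)], back-transformed, with p and SE the pooled values. State a fallback for a pooled rate of exactly 0% or 100%.

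Leave the CMH test and the CMH-weighted interval for the difference as they are.

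The cost is a short text change, a different interval option for the count-based rates, and a small extra step for the pooled ones. Upper limits at low counts become somewhat higher (7.2% instead of 3.9% for 1/75). Clopper-Pearson is somewhat conservative (97.6% at 6%). Wilson is closer to 95% on average but dips to 92.9% within 4–8%.

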5.2.2. Analyses of Non-Longitudinal Continuous Data

The non-longitudinal continuous data will be analyzed by Analysis of Covariance (ANCOVA) with treatment as the factor and randomization strata (baseline disease severity and age category) as covariates. When modeling the change from baseline values, the variable for visit will start with the first post-baseline visit, and the actual baseline value will be included as a covariate. At each visit, estimates of least square mean (LSM) values and the LSM differences between the PF-04965842 treated groups and the placebo group will be derived from the model. The corresponding p-values and 95% confidence intervals will also be derived from the model. The corresponding p-values and 95% confidence intervals will also be derived from the model. Estimates of the difference in LSMs along with the two-sided 95% confidence interval will also be provided for the PF-04965842 200 mg QD group versus the PF-04965842 100 mg QD group. No hypotheses will be tested.

5.2.3. Analyses of Longitudinal Continuous Data

Mixed-effect, repeated measures (MMRM) models will be used. The fixed effects of treatment (PF-04965842 200 mg QD and 100 mg QD and the placebo group), visit (Weeks 2, 4, 8 and 12), treatment-by-visit interaction and randomization stratification factors will be included. Visit will be modeled as a categorical covariate. Unstructured covariance matrix will be assumed for the model errors. Compound symmetry covariance matrix will be used if the model with unstructured covariance doesn't converge.

When modeling the change from baseline values, the variable for visit will start with the first post-baseline visit, and the actual baseline value will be included as a covariate. At each visit, estimates of least square mean (LSM) values and the LSM differences between the PF-04965842 treated groups and the placebo group will be derived from the model. The corresponding p-values and 95% confidence intervals will also be derived from the model.

Estimates of the difference in LSMs along with the two-sided 95% confidence interval will also be provided for the PF-04965842 200 mg QD group versus the PF-04965842 100 mg QD group. No hypotheses will be tested.

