9.2.2. Testing Procedure for Multiple Comparisons

There are five key hypotheses to be tested for each of the two PF-04965842 doses (200 mg QD and 100 mg QD) versus placebo, for the co-primary endpoints and two key secondary endpoints. The familywise Type-I error rate will be strongly controlled at 5% using a sequential, Bonferroni-based iterative multiple testing procedure.

The procedure will first test the co-primary endpoints (IGA and EASI75 at Week 12 for 200 mg QD vs placebo) at the 5% level. If this hypothesis is not rejected, then no further testing will be conducted. If this hypothesis is rejected, then testing may continue on two paths:

- The hypothesis for severity of pruritus (200 mg QD vs placebo at Week 2) will be tested at the 2.5% level. If this hypothesis is rejected, then the unused alpha level of 2.5% will be passed on to the testing for the key secondary endpoints and the co-primary endpoints for 100 mg QD vs placebo, in the order specified in Sequence A at a 5% significance level (see figure below). Testing stops at any point where a hypothesis cannot be rejected.
- If the hypothesis for severity of pruritus (200 mg QD vs placebo at Week 2) is not rejected at the 2.5% level, then the hypotheses for the key secondary endpoints and the co-primary endpoints for 100 mg QD vs placebo, in the order specified in Sequence A will be tested at a 2.5% significance level (see figure below). If all hypotheses in this sequence are rejected, then the unused alpha level of 2.5% will be passed on to the testing of the hypothesis for severity of pruritus (200 mg QD vs placebo) at Week 2 at the 5% level.

Figure 2. Schematic for Multiple Testing Procedure

The figure above illustrates the procedure showing the sequence of the tests.

Hypotheses for all other endpoints not described here are to be tested at the 5% level, without making adjustments for multiple comparisons.

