3.2. Secondary Efficacy Endpoints

3.2.1. Key Secondary Efficacy Endpoints

The key secondary efficacy endpoints are:

- Response based on ≥ 4 points improvement from baseline in the pruritus NRS (NRS4) for severity at Weeks 2, 4, and 12;
- Change from baseline in PSAAD at Week 12.
- Detailed descriptions of how the pruritus NRS and PSAAD scores are derived are provided in [Appendix 8](#) and [Appendix 10](#), respectively.

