6.3.2. Week 12 Change from Baseline in PSAAD

- Summary: Change from baseline at Week 12.
- Population: FAS, PPAS.
- Statistical Method: MMRM in [Section 5.2.3](#). As PSAAD is collected daily, data will be summarized weekly using a simple average of the values recorded within a week. In the implementation of the MMRM models, data from all weekly visits will be used
- Missing Data: Observed Data

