Appendix 10. Pruritus and Symptoms Assessment for Atopic Dermatitis (PSAAD) (e-Diary)

The PSAAD is a daily patient-reported symptom diary. The preliminary version is a 15-item questionnaire that includes 11 items developed to measure symptoms of atopic dermatitis, capturing those identified by patients to be most important, based on a 24-hour recall. Analysis of the PSAAD will be based solely on these 11 items. Four additional items were added for exploratory and psychometric validation purposes (Sleep & Usual Activities Questions and Patient Global Impression of Severity [PGIS] & Patient Global Impression of Change Questions [PGIC]).

The PSAAD total score for each day will be calculated as the simple arithmetic mean of items 1-11 as listed below. Items 12, 13, 14, and 15 will be only used to further validate PSAAD and they are not the part of the PSAAD scale itself.

For analyses included in this SAP, weekly averages of the PSAAD score will be used. For example, the baseline value is defined as a simple average of all observed values from Day -6 until Day 1, the Week 1 value is defined as a simple average of all observed values from Day 2 until Day 8, the Week 2 value is defined as a simple average of all observed values from Day 9 until Day 15, and so on and so forth up to Week 12.

Pruritus and Symptoms Assessment for Atopic Dermatitis (PSAAD)

Please answer each question by thinking about your skin condition (most often called atopic eczema or atopic dermatitis) over the past 24 hours. This includes today and last night.

For each question, think about all the areas of your body affected by your skin condition and choose the number that best describes your experience.

1) How itchy was your skin over the past 24 hours?

0	1	2	3	4	5	6	7	8	9	10
Not itchy										Extremely itchy

2) How painful was your skin over the past 24 hours?

0	1	2	3	4	5	6	7	8	9	10
Not painful										Extremely painful

3) How dry was your skin over the past 24 hours?

0	1	2	3	4	5	6	7	8	9	10
Not dry										Extremely dry

4) How flaky was your skin over the past 24 hours?

0	1	2	3	4	5	6	7	8	9	10
Not flaky										Extremely flaky

5) How cracked was your skin over the past 24 hours?

0	1	2	3	4	5	6	7	8	9	10
Not cracked										Extremely cracked

6) How bumpy was your skin over the past 24 hours?

0	1	2	3	4	5	6	7	8	9	10
Not bumpy										Extremely bumpy

7) How red was your skin over the past 24 hours?

0	1	2	3	4	5	6	7	8	9	10
Not red										Extremely red

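### The only fallback for the 12-visit PSAAD model is compound symmetry with no standard-error method, so the Week 12 test could be miscalibrated if it is used

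*SAP*

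**What the plan says.** SAP 5.2.3 fits an MMRM with treatment, visit, treatment-by-visit, stratification factors and baseline, and assumes an unstructured covariance. Its one contingency is "Compound symmetry covariance matrix will be used if the model with unstructured covariance" does not converge. For inference it says only that the "p-values and 95% confidence intervals will also be derived from the model". SAP 5.3.2 adds REML, which fixes how parameters are estimated but not how standard errors or degrees of freedom are obtained. Protocol 9.2.4 adds nothing on this.

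SAP 5.2.3 lists four visits (Weeks 2, 4, 8 and 12). For PSAAD, however, SAP 6.3.2 refers back to 5.2.3 and states: "In the implementation of the MMRM models, data from all weekly visits will be used". SAP Appendix 10 defines weekly averages from Week 1, "and so on and so forth up to Week 12". The PSAAD model therefore has 12 visits. Footnote v of the Protocol's Schedule of Activities restricts PSAAD to selected countries and gives no number of subjects.

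"Change from baseline in PSAAD at Week 12" is a key secondary endpoint (SAP 3.2.1). Protocol 9.2.2 says: "There are five key hypotheses to be tested for each of the two PF-04965842 doses", with strong familywise control at 5%. Depending on the Week 2 itch result for 200 mg, Sequence A is run at 5%, or the "series of testing in Sequence A (see Figure 2 below) will be tested at a 2.5% significance level".

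**The concern.** Compound symmetry forces one residual variance on all 12 weeks and one correlation on all pairs of weeks. Early post-baseline values usually track baseline closely and later ones less so. After baseline adjustment, residual variance may therefore grow towards Week 12, the only week that is tested. A model-based standard error that averages over weeks is then too small at Week 12.

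What is at stake is the type I error of one alpha-controlled key secondary test per dose. PSAAD's place in Sequence A is in a figure that is not shown, so the effect on later tests and on the familywise rate cannot be sized.

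**Working it through.** **The plan's own figures.** The documents give no power, SD or correlation for PSAAD. Their only power statement concerns the co-primaries (Protocol 9.1: "A total sample of 375 subjects with 150 subjects randomized to PF-04965842 200 mg QD", 150 on 100 mg and 75 on placebo). A two-sided 5% pooled normal approximation with 150 vs 75 gives 97.8% for IGA (26% vs 6%) and 99.8% for EASI-75 (45% vs 15%). Power for both is at least 97.8 + 99.8 − 100 = 97.6%. All three meet the stated floors of 95%, 99% and 94%. They do not bear on PSAAD.

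**Covariance parameters.** Four visits: 4 × 5 / 2 = 10. Twelve visits: 12 × 13 / 2 = 78. This shows the model is larger than 5.2.3 suggests. It does not show that the model will fail.

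**Closed form, given that the fallback is used with model-based errors.** With complete data, compound symmetry still estimates the Week 12 effect by the baseline-adjusted Week 12 difference, but its standard error uses the mean residual variance. With v(t) the residual variance at week t:

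- SE ratio r = √(mean v(t) / v(12))
- actual type I error = 2[1 − Φ(z·r)], with z = 1.960 (nominal 5%) or 2.241 (nominal 2.5%).

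Assume raw variance 1 at every week and correlation a + (1 − a)φ^lag. The SAP lists no baseline-by-visit term, so the baseline slope is common: b = mean ρ(t), where ρ(t) is the correlation of baseline with week t, and v(t) = 1 − 2bρ(t) + b².

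Example, a = 0.5, φ = 0.9: b = 0.769; mean v = 1 − b² = 0.4085; ρ(12) = 0.6412; v(12) = 1 − 2(0.769)(0.6412) + 0.5915 = 0.605; r = √(0.4085/0.605) = 0.822. Type I error is 2[1 − Φ(1.610)] = 10.7% at nominal 5% and 6.6% at nominal 2.5%.

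| Assumed structure | Nominal 5% | Nominal 2.5% |
|---|---|---|
| a = 0.3, φ = 0.95 | 12.3% | 7.8% |
| a = 0.5, φ = 0.9 | 10.7% | 6.6% |
| a = 0.5, φ = 0.8 | 8.3% | 4.7% |
| a = 0.7, φ = 0.5 | 5.9% | 3.1% |
| residual SD rising 1.5 to 1.8 | 7.2% | 4.0% |
| residual SD flat | 5.0% | 2.5% |
| residual SD falling 1.8 to 1.5 | 3.1% | 1.4% |

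Over a grid with equal raw variance and baseline to Week 12 correlation 0.5-0.8, nominal 5% becomes about 10-14% for φ 0.90-0.98, 6.9-9.8% for φ 0.70-0.85 and 5.3-6.4% for φ 0.30-0.60.

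**Simulation.** 150/150/75, 10,000 runs per case, complete data, REML compound symmetry with baseline and two strata factors (assumed 35% severe, 15% adolescent). Type I error at nominal 5% / 2.5%:

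| Case | Model-based SE | CR2 SE with t reference |
|---|---|---|
| a = 0.3, φ = 0.95 | 12.6 / 8.0 | 5.2 / 2.5 |
| a = 0.5, φ = 0.9 | 10.5 / 6.3 | 4.9 / 2.4 |
| a = 0.5, φ = 0.8 | 7.9 / 4.5 | 4.8 / 2.6 |
| a = 0.7, φ = 0.5 | 6.0 / 3.0 | 5.2 / 2.4 |
| constant correlation 0.6 | 4.9 / 2.1 | 5.0 / 2.3 |
| a = 0.3, φ = 0.95, raw SD falling 40% | 7.0 / 3.9 | 5.0 / 2.7 |

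A separate simulation with 12% random dropout (1,000 runs per case) gave 12.5-13.7% for AR(1) correlation 0.90-0.98 and 5.4% when compound symmetry was true. An uncorrected sandwich error gave 4.5-6.1% over its seven cases.

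**Small samples.** The PSAAD number is not given, so smaller sizes were tried at nominal 5%. An uncorrected sandwich with a normal reference gave 6.2-6.9% at 40/40/20 and 7.1-7.9% at 24/24/12. CR2 with Satterthwaite degrees of freedom gave 4.8-5.3% and 4.8-5.4%.

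**Changing the structure alone.** With a = 0.3, φ = 0.95 at 150/150/75, model-based errors gave 10.0% under heterogeneous AR(1) and 8.8% under heterogeneous Toeplitz. With CR2 these were 4.8% and 5.1%.

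**The case against.** The trigger may never occur. In 510 fits of the 12-visit unstructured REML model to simulated Gaussian data, with 12% dropout or with 25% dropout plus 3% intermittent gaps, all 510 converged, 120 of them at only 24/24/12. That rests on one fitting routine and assumed missingness, but it suggests that non-convergence is uncommon. This stands.

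The 10-14% figures also come from one part of the assumption space. PSAAD is a mean of 0-10 items, and its spread may shrink as scores fall. With raw SD falling linearly by 30% to Week 12, the same formula gives 8.5%, 6.9%, 4.6% and 2.7% for the four decaying-correlation structures in the order tabulated; with a 40% fall it gives 7.2%, 5.6%, 3.4% and 1.8%. These figures are correct: for two of the four structures the test becomes conservative. The direction is therefore unknown.

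The remedy is less tested for the structures it puts first. Heterogeneous Toeplitz was run in one scenario (1,600 runs) and gave 5.8% with CR2 at 24/24/12. The ladder was not simulated as a whole, and the degrees of freedom were a Welch approximation from arm sizes. These limits also stand.

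Finally, the SAP already has a deterministic rule. But that rule leaves the standard error open, and when used with model-based errors it can be wrong in either direction. Rarity lowers the priority of the point without removing it.

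**Conclusion.** The point holds as a minor one. Compound symmetry is the only named fallback, no standard-error method is given, and the PSAAD model has 12 visits rather than the four listed in 5.2.3. The Week 12 p-value is too small only if the unstructured fit fails, model-based errors are then used, and residual variance at Week 12 exceeds the average over weeks. Under those conditions, type I error at nominal 5% runs from just above 5% to about 14% in the closed-form grid. With flat variance it is nominal, and with falling variance it is below nominal. Every variance, correlation, dropout rate and PSAAD sample size behind these figures is an assumption, because the documents supply none. The co-primary analyses use CMH and are not affected.

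**What to change.** Replace the compound symmetry sentence in SAP 5.2.3 with:

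> If the unstructured model does not converge, heterogeneous Toeplitz, then heterogeneous AR(1), then compound symmetry will be fitted in that order and the first that converges used. For any structure other than unstructured, the bias-reduced (CR2) empirical (sandwich) standard error and a t reference distribution with Satterthwaite degrees of freedom will be used.

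All weekly visits stay in the model, as SAP 6.3.2 requires. The robust standard error is the essential part. It corrects the variance only, not bias from a misspecified covariance when dropout is MAR, which is why the more flexible structures come first.

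The cost is a few lines of text and code before unblinding, with no effect if the unstructured model converges. If compound symmetry is in fact true, type I error stays nominal (4.9-5.0%). The Week 12 confidence interval widens by about 0.5% at 150/150/75 (t quantiles 1.976/1.966), 2% at 40/40/20 (2.024/1.986) and 3% at 24/24/12 (2.074/2.005). The standard error is also somewhat less stable if the selected-countries sample is small.
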